CLINICAL PROTOCOL

**PROSPECTIVE RANDOMIZED 12-WEEK CONTROLLED STUDY OF VISUAL
FIELD CHANGE IN SUBJECTS WITH PARTIAL SEIZURES RECEIVING
PREGABALIN OR PLACEBO**

Compound:	PD-0144723; CI-1008
Compound Name (if applicable):	Pregabalin
EudraCT Number	2009-014269-25
US IND Number (if applicable):	49,393
Protocol Number:	A0081096
Phase:	Phase IV

This document contains confidential information belonging to Pfizer. Except as otherwise agreed to in writing, by accepting or reviewing this document, you agree to hold this information in confidence and not copy or disclose it to others (except where required by applicable law) or use it for unauthorized purposes. In the event of any actual or suspected breach of this obligation, Pfizer must be promptly notified.

Document History

Document	Version Date	Summary of Changes and Rationale
Amendment 5	25 September 2020	
Sample size estimation changed based on the observed common standard deviation of mean deviation. Common SD changed from 5.6 dB based on literature at the time of the study design to 1.3 dB based on observed blinded data from study A0081096.
 
Enrollment to be approximately 187.
 
The following statement has been added to the Section 9.4 of the protocol: the expectation is that the Per Protocol subset will be close in the number of subjects to the number of subjects randomized.

Amendment 4	15 December 2015	
Single Reference Safety Document (SRSD) for this study was changed from the Core Data Sheet (CDS) to the Investigators Brochure (IB). The IB contains more extensive information about pregabalin than the CDS.
 
The protocol introduction was updated to include current marketing information on Lyrica.
 
The following changes were made to comply with FDA and Neuropsychiatric and Abuse Potential Advisory Council (NAPAC) Guidance:
 
 • Suicidality assessment: the Columbia-Suicide Severity Rating Scale (C-SSRS) will be performed instead of the Sheehan-Suicidality Tracking Scale (S-STTS) for subjects screened following approval/initiation of Amendment 4. Subjects who are randomized under Amendment 3 will not switch to the C-SSRS. • Suicidal Behaviors Questionnaire–Revised (SBQ-R) will be performed at screening. • Scoring instructions for the PHQ8 have been inserted as well as a reference to the Instruction Manual. 
The following protocol exclusion has been inserted to increase subject safety:

	
• Any subject at risk of suicide or self-harm based on investigator judgment and/or details of a mental health risk assessment (MHRA) by a qualified mental health professional. 
Instructions for completion of the PHQ-8 have been included. The Instruction Manual has been referenced.
 
The following statement has been inserted into Section 4.3 to reinforce the requirement to include only subjects who have adequate baseline VFT.
 
• Subjects may not be randomized prior to receiving confirmation of the validity of the Baseline VFT from the central reader. 
Sections presenting the Visual Field Testing (VFT) procedures were revised to clarify procedures or to amend the procedures to make it easier for the investigator to comply with the protocol:
 
• Repeat VFT should be performed as soon as possible and within 2 weeks following notification from the central reader.• Section has been updated to reflect the electronic submission of the VFT results with subsequent faster response times. 
The number of sites to participate in the study has been deleted. This study has been ongoing for many years with waves of sites being initiated and terminated.
 
The following changes were made to comply with the current protocol template and required language/wording:
 
• Abbreviation list moved to an Appendix.• Updated terms study drug and study medication to investigational product for consistency.• Inserted Lifestyle Guidelines which includes template contraception language.• Inserted Sponsors Medically Qualified
--	--

		
Personnel.
 
 • Updated Trial Treatments including insertion of new sections for Investigational Product Storage, Investigational Product Accountability and Destruction of Investigational Product Supplies. • Updated Drug Supplies. • Updated Investigational Product Storage. • Updated Quality Control and Quality Assurance. • Inserted Medication Errors. • Updated Exposure During Pregnancy. • Inserted Occupational Exposure. • Updated Publication of Results. 
The following changes were made to clarify potentially confusing language or to streamline the protocol:
 
Clarified dose administration.
 
Deleted samples of S-STs and PHQ-8 from Appendices.
 
Subjects will be required to record all investigational product dosing in a dosing diary which is to be reviewed by site staff with the subject at each visit. This is expected to improve the ability of the investigative site to reconcile investigational product use.

Amendment 3	12 December 2011	
To add new safety wording. To allow for rescreening of subjects. To add clarification around the timing of the visual field testing (VFT) and handling of the primary endpoint as an AE. Also clarification of prohibited and allowed concomitant medications; and documentation of adverse events related to changes from entry in vital signs, weight and on the physical exam.
 
Background & Rationale, PASS language added, Subject Selection, Compliance, DMC text added.

Amendment 2	12 August 2009	See Appendix 4.

Amendment 1	17 October 2006	See Appendix 3.
Original protocol	25 May 2006	N/A

This amendment incorporates all revisions to date, including amendments made at the request of country Health Authorities, IRB/ERB, etc.

SUMMARY

Indication:

Epilepsy; adjunctive therapy in patients with partial seizures.

Rationale:

[figure not shown]
This study is being performed as a Phase IV commitment to assess visual fields in subjects taking pregabalin as compared to placebo when added to their existing antiepileptic therapy.

Objectives:

To evaluate visual fields in subjects with partial epilepsy receiving 12 weeks treatment of pregabalin compared to placebo.

Trial Design:

This is a Phase IV, multicenter, randomized placebo-controlled trial to further characterize visual fields in subjects with partial epilepsy dosed for 13 weeks, including a 1 week up titration and 1 week down titration from the target dose of pregabalin 300 mg/day versus placebo. Comprehensive ophthalmologic testing will be done at pre-treatment baseline to exclude those with pre-existing eye disease.

Approximately 187 subjects will participate in the study. Subjects will be randomized 1:1 to pregabalin or placebo, with approximately 93 randomized to pregabalin and 93 to placebo.

Endpoints:

The primary endpoint is the proportion of subjects with a decrease in the threshold value from baseline to termination in five or more points (in either eye) at the $p < .05$ level repeated in the same five points on subsequent computerized automated perimetry testing (Humphrey 24-2 SITA standard).

Trial Treatments:

Subjects will receive oral pregabalin 75 mg twice daily (BID) (150 mg/day) or matching placebo for titration and taper. Subjects will receive oral pregabalin 150 mg BID (300 mg/day) or matching placebo for the treatment phase.

Statistical Methods:

The primary endpoint will be analyzed using a non-inferiority analysis. The difference in proportions between pregabalin and placebo in the per protocol population will be compared using a 2-sided 95% confidence interval (CI). Non-inferiority will be demonstrated if the upper CI bound is less than 0.10 (10%). The proposed sample size will have >90% power to detect non-inferiority on the primary endpoint, assuming a proportion of 1% for each group.

SCHEDULE OF ACTIVITIES

Protocol Activity	Screening	Baseline	Wk 0 Randomization	Wk 1	Wk 6	Wk 12 (Or ET)	Week 15 (Follow-Up)
Visit Number ⁿ	1	2	3 ^m	4	5	6	7
Informed Consent	X						
Inclusion/Exclusion Criteria	X	X	X				
Review/document contraception use	X						
History/Diagnosis/Demographics	X						
Physical Examination ^p	X					X	
Concomitant Medication	X	X	X	X	X	X	X
Body Weight	X	X		X	X	X	X
Vital Signs (Sitting BP/HR)	X	X		X	X	X	
ECG (Singlet)	X						
EEG	X ^a						
CT or MRI	X ^b						
Clinical	1) Hematology ^c	X				X	
Laboratory	2) Chemistry ^d	X				X	
	3) Urinalysis ^e	X				X	
Urine Pregnancy Test ^f	X					X	
Urine Drug Screen	X						
Ophthalmic Examination	1) External Eye Exam	X				X	X ^g
	2) ETDRS Acuity	X	X		X	X	X ^g
	3) Intraocular Pressure	X					
	4) Dilated Funduscopic	X					
	5) VFT (24-2 SITA)	X ^{h,i}	X ^{h,i}			X ^h	X ^h
Patient assessment of seizure frequency						X	

Protocol Activity	Screening	Baseline	Wk 0 Randomization	Wk 1	Wk 6	Wk 12 (Or ET)	Week 15 (Follow-Up)
Investigational product Dispensing			X ^{i,j}	X ^k	X ^k	X ^j	
Dispense Dosing Diary			X		X		
Review Dosing Diary with subject				X	X	X	X
Sheehan-Suicidality Tracking Scale (S-STSS) ^{o,r}	X	X	X	X	X	X	X
Columbia-Suicide Severity Rating Scale (C-SSRS) ^{o,r}	X	X	X	X	X	X	X
Suicidal Behaviors Questionnaire – Revised (SBQ-R) ^r	X						
Patient Health Questionnaire–8 (PHQ-8)	X						
Assessment of need to complete a risk assessment ^q	X	X	X	X	X	X	X
Adverse Events Report			X			X	

- a. Subjects who have not had a test within 2 years. See inclusion criteria 1.
- b. Subjects who have not had a test within 3 years. See inclusion criteria 4.
- c. Hemoglobin, hematocrit, RBC count, WBC count, platelet count.
- d. Electrolytes (Na, K, Ca, Cl, bicarbonate), creatinine, BUN, glucose, AST, ALT, alkaline phosphatase, bilirubin, CK, uric acid, albumin, total protein.
- e. Specific gravity, PH, Glucose (qual), Protein (qual), Blood (qual), Ketones, Nitrite and Microscopy if urine dipstick is positive for blood or protein.
- f. Childbearing potential female subjects only.
- g. Subjects who have had visual findings on Week 12 and subsequently confirmed.
- h. A repeat may be necessary upon the confirmation from central reader.
- i. Recommend subject to take first dose in the evening.
- j. Titration/tapering dose.
- k. Treatment dose.
- l. Conduct 2 tests.
- m. Usually occur between the 3rd – 7th day after Baseline (Visit 2) when the verification of VFT is available.
- n. Screening procedures can be completed within 21 days prior to Baseline; Study Visits 4 – 7 have a ±3 days window.
- o. The “Lifetime” assessment is completed at Screening and the “Since Last Visit” assessment is completed at **all** other visits.
- p. Including neurological exam at screening.
- q. A risk assessment must be performed and documented if the subject meets the criteria detailed in Protocol.
- r. Subjects screened/randomized under Amendment 3 will continue the S-STSS for assessment of suicidal ideation and behaviour. Subjects screened /randomized under Amendment 4 will have suicidal ideation and behaviour assessed by the C-SSRS and the SBQ-R.

TABLE OF CONTENTS

SCHEDULE OF ACTIVITIES.....	7
LIST OF TABLES	12
APPENDICES	12
1. INTRODUCTION	13
1.1. Background	13
1.2. Rationale.....	14
2. TRIAL OBJECTIVES AND ENDPOINTS	14
2.1. Objective	14

1. INTRODUCTION

1.1. Background

Pregabalin (Lyrica®) has been approved in over 130 countries to date for varying neuropathic pain indications and for adjunctive treatment of patients with partial seizures and for generalized anxiety disorder. Lyrica is approved in the United States for management of neuropathic pain associated with diabetic peripheral neuropathy or postherpetic neuralgia, for the adjunctive treatment of adult patients with partial onset seizures, and for management of fibromyalgia.¹ Lyrica is approved in European Union countries for the treatment of peripheral neuropathic pain, adjunctive treatment of partial seizures with or without secondary generalization, and for the treatment of generalized anxiety disorder.² Since initial market approval of Lyrica in 2004 through 2014, it is estimated that more than 28.5 million patient years of exposure will have accumulated worldwide. More detailed information, including efficacy results in adults and the possible risks associated with administration of pregabalin, can be found in the current Investigator Brochure (IB).

Prospectively planned ophthalmologic assessments, including visual acuity testing, formal visual field testing and dilated funduscopy examination, were performed in the pregabalin clinical development program for all of the initial indications.

Formal visual field testing was conducted in over 2400 patients treated with pregabalin for neuropathic pain, chronic pain syndromes, intractable epilepsy, or generalized anxiety disorder in randomized controlled clinical trials of up to 3 months in duration and in over 3600 patients in open-label trials of up to 4 years in duration. Ophthalmologic assessments were included in the program due to concerns expressed at the time on emerging reports of visual field disturbances with the anticonvulsant vigabatrin, a gamma-aminobutyric acid (GABA)-transaminase inhibitor.³⁻¹¹ The mechanism of the visual field defects with vigabatrin is unknown but was considered as possibly related to its GABA mechanism. As a structural derivative of GABA, regulatory agencies considered similarity of pregabalin to vigabatrin as possible. Subsequently, it became clearer that the mechanism of action of pregabalin was not related to GABA-transaminase inhibition or to a GABA related mechanism. While the mechanism of action of pregabalin is not completely understood, results in animal models indicate that binding to the alpha-2-delta subunit of voltage-gated calcium channels may be involved in the activity of pregabalin.

In controlled pregabalin studies, a higher proportion of patients treated with pregabalin reported blurred vision (6%) than did patients treated with placebo (2%), which resolved in the majority of patients during treatment. In patients assessed with prospectively planned ophthalmologic testing, visual acuity was reduced in 7% of patients treated with pregabalin, and 5% of placebo-treated patients. Visual field changes were detected in 13% of pregabalin-treated, and 12% of placebo-treated patients. Funduscopy changes were observed in 2% of pregabalin-treated and 2% of placebo-treated patients.

This study is a Post-Authorization Safety Studies (PASS). It is being conducted as a commitment agreed upon with the United States Federal Drug Administration (FDA) regulatory agency.

1.2. Rationale

This study is being performed to further characterize visual fields with pregabalin as compared to placebo when added to their existing antiepileptic therapy. In this study, standardized test equipment, program and test procedures across all study sites will be used to optimize the data quality and the sensitivity of the test. Threshold visual fields will be performed using computerized static perimetry.

Complete information for this compound may be found in the Single Reference Safety Document (SRSD), which for this study is the pregabalin Investigator's Brochure (IB). The SRSD will be used in determining expected versus unexpected adverse events.

2. TRIAL OBJECTIVES AND ENDPOINTS

2.1. Objective

To evaluate visual fields in subjects with partial epilepsy receiving 12 weeks treatment of pregabalin compared to placebo.

2.2. Endpoints

Primary endpoint:

- The proportion of subjects with a decrease in the threshold value from baseline to termination in five or more points (in either eye) at the $p < .05$ level repeated in the same five points on subsequent computerized automated perimetry testing (Humphrey 24-2 SITA standard).

Secondary endpoints:

- Change in mean deviation score from baseline to Week 12 from the Humphrey threshold test;
- Change in visual acuity from Baseline to Week 12 expressed by number identified in ETDRS visual acuity assessment.

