6. TRIAL PROCEDURES

6.1. Screening

At the Screening Visit (up to 21 days prior to Baseline), subjects will be eligible for the study after verification of the inclusion/exclusion criteria and the study has been explained to them. The following procedures will be completed at the screening visit:

- Obtain written informed consent (must be signed prior to the initiation of any study related activities);
- Verify inclusion/exclusion criteria;
- Record demographic information, medical history, and diagnosis;
- Record concomitant medications;
- Perform physical exam including neurologic exam;
- Collect vital signs (sitting blood pressure, heart rate);
- Perform electrocardiograph;
- Prescribe/perform EEG, CT and MRI if necessary (inclusion criteria 1 and 4);
- Collect body weight;
- Collect blood samples for clinical laboratories;
- Blood chemistry;
- Hematology;
- Urinalysis including drug screen;
- Urine pregnancy test (females of child-bearing-potential);
- Columbia-Suicide Severity Rating Scale (C-SSRS) Lifetime Assessment;
- Suicide Behaviors Questionnaire-Revised (SBQ-R);

- Patient Health Questionnaire – 8 (PHQ-8);
- Determine if mental health risk assessment (MHRA) is required (refer to [Section 7.5](#));
- Ophthalmic Examination.
 1. External eye examinations.
 2. Best corrected ETDRS visual acuity.
 3. Intraocular pressure to be measured by a calibrated applanation tonometer such as Goldmann, Perkins, or Tonopen.[®] If more than one tonometer is available at the site, the same one should be used consistently throughout the study.
 4. Computerized automated perimetry (Humphrey 24-2 SITA standard) 2 times on both eyes with a minimum 5 minute break between each eye tested and minimum 10 minutes (may take longer break if needed) between 2 tests.
 5. Dilated fundoscopic examination. Recommend subject to wear sunglasses for at least one hour after this procedure and to bring someone along for driving home.

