7.1.3. Best Corrected Visual Acuity

The best corrected visual acuity (with glasses or best possible glasses prescription) will be measured using the ETDRS charts. The letters on chart A are read using the right eye and chart B using the left eye.

The subject starts the top of the chart and begins to read down the chart. The subject reads down the chart until they reach a row where a minimum of three letters on a line cannot be read. The subject is scored by how many letters could be correctly identified.

The number of correct letters identified by each eye will be collected into the CRF.

Visual acuity will be measured at Screening (Visit 1), Baseline (Visit 2), Week 6 (Visit 5), and Week 12 (Visit 6) visits, and at Week 15 (Follow-up, Visit 7) visit if deemed necessary. The best corrected visual acuity should be obtained at each scheduled visit or repeat visit. It should not be copied from a previous visit.

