9.4.2. Analysis of Secondary Endpoints

9.4.3. Mean Deviation

Change in mean deviation from baseline to termination will be computed for each subject. Baseline mean deviation will be the average of the two mean deviations from the Baseline visit, and termination mean deviation will be the mean deviation at the Week 12 visit (or the last available after Day 1 for subjects who terminate early). If a repeat test was done at termination, the mean deviation from the repeat test will be used. For each subject, the worst eye (ie, the eye with the greatest decrease in mean deviation) will be used in the analysis. Change in mean deviation will be analyzed for the ITT population using analysis of covariance (ANCOVA), with treatment and center in the model and the baseline mean deviation as the covariate. Least squares means will be obtained from the model and a

2-sided 95% confidence interval will be constructed on the difference in least squares means between pregabalin and placebo. Non-inferiority with respect to mean deviation will be demonstrated if the lower bound of the CI is greater than -2.0 dB.

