9.4.4. Visual Acuity

Visual acuity (best-corrected, measured using ETDRS charts) is expressed in terms of number of letters correctly identified. Change in visual acuity from baseline to termination will be computed for each subject. Baseline will be defined as the last visual acuity assessment prior to receiving investigational product, and termination will be the visual acuity assessment at the Week 12 visit (or the last available after Day 1 for subjects who terminate early). If acuity was assessed at a repeat visit at termination, the acuity from the repeat test will be used. For each subject, the worst eye (ie, the eye with the greatest decrease in visual acuity) will be used in the analysis. Change in visual acuity will be analyzed for the ITT population using ANCOVA, with treatment and center in the model and the baseline acuity as the covariate.

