6.4. Covariates

The covariate for Mean Deviation is the baseline MD, which is the average of the two mean deviations from the Baseline visit.

The covariate for Visual Acuity is the baseline visual acuity, defined as the last visual acuity assessment prior to receiving study medication.

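### The visual acuity ANCOVA leaves out the Screening letter count, so the between-arm interval is somewhat wider than the collected data allow (lost efficiency, not bias)

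*Protocol*

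**What the plan says.** Protocol 2.2 names the endpoint: "Change in visual acuity from Baseline to Week 12 expressed by number identified in ETDRS visual acuity assessment". The operative rule is in Protocol 9.4.4: "Baseline will be defined as the last visual acuity assessment prior to receiving investigational product". SAP 6.2 and 8.2.2 repeat it, and SAP 6.4 applies it to the model: "The covariate for Visual Acuity is the baseline visual acuity, defined as the last visual acuity assessment prior to receiving study medication". One reading therefore serves three purposes: it is subtracted to form the change, it decides which eye shows the greater decrease, and it is the ANCOVA covariate beside treatment and center.

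Two pre-dose readings exist. Protocol 7.1.3 states: "Visual acuity will be measured at Screening (Visit 1), Baseline (Visit 2), Week 6 (Visit 5), and Week 12 (Visit 6) visits". It adds "The number of correct letters identified by each eye will be collected into the CRF" and, on taking a new reading at each visit, "It should not be copied from a previous visit". Screening lies up to 21 days before Baseline (Protocol 6.1), and no investigational product is given in between.

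For comparison, Protocol 9.4.3 says of mean deviation: "Baseline mean deviation will be the average of the two mean deviations from the Baseline visit". Both of those tests come from the Baseline visit.

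**The concern.** A single letter count carries its full measurement error into the change score, and as a covariate it predicts the Week 12 count less well than two readings would. The second reading has already been collected in the same eye, before treatment. Leaving it out gives up some precision for nothing in return.

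Visual acuity is a named secondary endpoint of a post-authorization safety study. Protocol 1.1 reports reduced acuity in 7% of pregabalin and 5% of placebo patients in earlier controlled studies. Neither document gives acuity a margin, SD or power, so what the analysis offers is the estimated difference and its interval. The width of that interval is the only thing at stake.

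**Working it through.** **The plan's own figure.** None is stated for acuity. The nearest is mean deviation (Protocol 9.1, Table 1): SD 1.3 dB, margin 2.0 dB, about 93 per arm, two-sided 95% interval. SE = 1.3 × √(2/93) = 0.191; 2.0/0.191 = 10.5; 10.5 − 1.96 = 8.5. Power is above 99.9%, as stated. This cannot be carried over to acuity.

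**Inputs.** About 187 subjects randomized 1:1 (Protocol 3); two pre-dose readings per eye (7.1.3); worst-eye change, with ANCOVA on treatment, center and baseline (9.4.4). Assumed, because the documents do not give it: the correlation *r* between two readings of the same eye, taken from 0.3 to 0.8.

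**Closed form, one eye.** Scale acuity to variance 1 and treat the readings as exchangeable. With one pre-dose reading in the model, the residual variance is 1 − r². With two, it is 1 − 2r²/(1 + r). The ratio is (1 + 2r)/(1 + r)². At r = 0.5 this is 0.667/0.750 = 0.889.

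**With the planned worst-eye rule.** Simulation of 93 v 94 subjects, two eyes, between-eye correlation of true acuity 0.7 (also assumed), center omitted, 4,000 runs, no true change over time. Entries are the variance of the treatment difference relative to the planned analysis.

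| r | Closed form | Screening count added as covariate | Mean of two as baseline |
|---|---|---|---|
| 0.3 | 0.947 | 0.959 | 0.876 |
| 0.5 | 0.889 | 0.924 | 0.855 |
| 0.7 | 0.830 | 0.887 | 0.819 |
| 0.8 | 0.803 | 0.856 | 0.779 |

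A repeat of the simulation gave 0.85 to 0.96 for the added covariate and 0.77 to 0.89 for the mean of two.

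For the added covariate, interval width scales by √0.959 = 0.979 to √0.856 = 0.925, so the interval is about 2% to 7% narrower. In sample-size terms this is 187/0.959 = 195 to 187/0.856 = 218 subjects under the planned model.

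**If subjects truly change over 12 weeks.** With subject-level change of SD 0.5 (in units of the acuity SD), the SE ratio for the added covariate is 0.962 to 0.987. Squared, that is 0.925 to 0.974, a variance gain of about 3% to 7%. With SD 1.0 the SE ratio is 0.979 to 0.994, squared 0.958 to 0.988, a gain of about 1% to 4%. For the mean of two, the SE ratios are 0.941 to 0.957 (SD 0.5) and 0.965 to 0.982 (SD 1.0).

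**If Screening is noisier than Baseline (r = 0.8).** With 1.5 times the error SD, the SE ratio for the mean of two is 0.96. With twice the error SD it is 1.04, a loss (variance ratio 1.07 to 1.10 across runs). The added covariate still gains there (variance ratio 0.95 to 0.96), because the model sets the weight of the Screening count.

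**Bias.** With a true effect of −0.30 SD in both eyes, the planned rule returned −0.299 and the mean of two returned −0.300.

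**The case against.** The strongest reply is that this is a preference, not an error. The last pre-dose reading is a conventional baseline and is defined the same way in every relevant section. With no margin or decision rule for acuity, a narrower interval changes no prespecified conclusion. All of that stands.

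A reader might infer that the plan treats acuity inconsistently, since mean deviation gets an averaged baseline. The documents do not support this. The two averaged mean deviations are both from the Baseline visit, where only one acuity test is listed (Protocol 6.2.1), and SAP 6.2 expressly keeps Screening values out of the visual field baseline. Redefining the acuity baseline to include Screening would make acuity the only ophthalmic endpoint built that way. The objection therefore counts against averaging. It does not count against a second covariate, which leaves the baseline definition alone.

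The size of the gain is also open to challenge. The larger figures need equally reliable readings and no true change over time. Screening is the first study exposure to the charts, and excluding acuity worse than 20/25 (Protocol 4.2) restricts the range, which tends to lower *r*. These are fair points, and they are why the range starts near 1%.

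Finally, the added covariate does nothing for the worst-eye choice. Choosing the worse of two noisy eyes produces an apparent decline even under no change: at r = 0.8, −0.36 SD in placebo with one baseline reading and −0.31 SD with the mean of two. The artefact is present in both arms, and in the simulations it did not bias the difference.

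**Conclusion.** The point holds as a modest loss of efficiency on a secondary endpoint. Adding the Screening count as a covariate lowers the variance of the acuity difference by roughly 1% to 15%. The upper end assumes r near 0.8, equally reliable readings and no true change; the lower end applies if subjects truly change. The correlation, the between-eye correlation and the amount of true change are all assumptions, and with no acuity SD in the documents the gain cannot be expressed in letters.

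Three stronger readings should not be drawn. The between-arm estimate is not biased. No power statement or non-inferiority conclusion is affected, since the powered endpoints are visual field deterioration and mean deviation. The same argument also gives no practical reason to add Screening values to the mean deviation model, whose stated power already exceeds 99.9%.

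Averaging the two readings gains about 11% to 23% in variance when they are equally reliable and nothing truly changes. It loses if Screening error is about twice Baseline error, so it should not replace the current baseline definition.

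**What to change.** Before unblinding, keep the acuity change score, the worst-eye rule and the baseline definition as they are. In Protocol 9.4.4 and SAP 6.4, 8.1, 8.2.2 and the table in 8.2.5, add the Screening letter count of the selected eye as a second covariate in the visual acuity ANCOVA. Three details need stating:

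- **Which attempt.** Rescreening is allowed (Protocol 3), so take the count from the successful screening attempt.
- **Which record.** Screening up to 21 days before Baseline, with randomization usually 3 to 7 days after it, puts Screening about 28 days before the first dose (21 + 7). Both readings then fall in the single Baseline window of days −99 to 1 in SAP A.1.1, so the Screening count should be picked by visit label.
- **Missing values.** Give a rule for a missing Screening count, so that no subject drops out of the model.

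As sensitivity analyses, report the planned single-covariate model and the version with the mean of the two readings as baseline.

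The cost is one degree of freedom, a few lines of code and a small wording change. Because Protocol 9.4.4 names the covariate, the protocol wording needs the amendment and IRB/IEC approval described in Protocol 12.1, and could be bundled with another change. No new data or visits are needed.
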